	
 3. SBP_{day} > 135 and ≤ 169 mmHg and DBP_{day} ≤ 110 mmHg at Day 0 (i.e., after the 10- to 14-day washout from prior BP medication); 4. Body Mass Index (BMI) of 18.5 to 34.9 kg/m²; 5. Healthy (other than hypertension) as determined by the Investigator based on medical history, physical examination, vital signs, 12-lead ECG, and clinical laboratory tests; 6. A negative pregnancy test at initial screening visit; 7. If WCBP, agree to use a highly effective form of birth control while on study (from Screening through final study visit); Highly effective methods of birth control are defined as those, alone or in combination, that result in a low failure rate (i.e., less than 1% per year) when used consistently and correctly. Forms of birth control include intrauterine device (IUD), birth control patch or vaginal ring, oral, or injectable or implanted contraceptives, or a vasectomized partner, or abstinence from sexual intercourse. Abstinence is acceptable only as true abstinence: when this is in line with the preferred and usual lifestyle of the subject. Periodic abstinence (e.g., calendar, ovulation, symptothermal, post-ovulation methods) and withdrawal are not acceptable methods of contraception. A woman that is postmenopausal (≥2 years since last menstrual period) or permanently sterilized (e.g. tubal occlusion, hysterectomy, bilateral salpingectomy) is not considered a WCBP. 8. Able to comprehend and sign an ICF. 
Exclusion Criteria
 
 1. Resting systolic BP > 169 mmHg or a resting diastolic BP > 110 mmHg at initial screening visit while on their standard antihypertensive therapy (where resting is defined as supine for at least 10 minutes with minimal interaction); 2. Weight < 55 kg; 3. Fragile health; 4. Evidence of clinically significant findings on screening evaluations (clinical, laboratory, and ECG) which, in the opinion of the Investigator would pose a safety risk or interfere with appropriate interpretation of safety data; 5. Current or recent history (within four weeks prior to initial screening visit) of a clinically significant bacterial, fungal, or mycobacterial infection; 6. Current clinically significant viral infection; 7. History of malignancy, with the exception of cured basal cell or squamous cell carcinoma of the skin; 8. Major surgery within four weeks prior to initial screening visit; 9. Presence of a malabsorption syndrome possibly affecting drug absorption (e.g., Crohn's disease or chronic pancreatitis); 10. Active peptic ulceration or history of gastrointestinal bleeding; 11. History of myocardial infarction, congestive heart failure, or stroke; 12. Any current cardiovascular disease (other than hypertension); 13. History of psychotic disorder; 14. History of alcoholism or drug addiction or current alcohol or drug use that, in the opinion of the Investigator, will interfere with the subject's ability to comply with the dosing schedule and study evaluations; 15. History of any illicit drug use within one year prior to initial screening visit; 16. Positive drug screen at initial screening visit. A positive drug screen for opiates only (with all other drug tests negative) will not be a basis for exclusion if the subject took over-the-counter narcotics as indicated on the product label within 24 hours prior to the drug screen; 17. Current treatment or treatment within 30 days prior to first dose of study drugs with another investigational drug or current enrollment in another clinical trial;

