21. Asthma, acute rhinitis, nasal polyps, angioneurotic oedema, urticaria or other allergic type reactions after taking acetylsalicylic acid or NSAIDs including cyclooxygenase-2 (COX-2) inhibitors;
22. Subjects who, in the opinion of the Investigator, are unable or unlikely to comply with the dosing schedule and study evaluations;
23. Pregnant or lactating;
24. Unable to correctly use ABPM after instruction on its use;
25. Subjects with Child-Pugh Class B or C cirrhosis;
26. Subjects currently taking a calcium channel blocker or any NSAID for any reason will be excluded. Subjects will not be withdrawn from these drugs to be enrolled in the trial;
27. Subjects that took a calcium channel blocker in the past for any indication;
28. Creatinine clearance < 50 ml/min as estimated by the Cockcroft-Gault equation*;

**Cockcroft-Gault equation:*

estimated creatinine clearance = (140 – age) X body weight (kg)/72 X P_{Cr} (mg/dL)

multiply by 0.85 for women

29. Known cytochrome P450 2C9 (CYP2C9) poor metabolizer;
30. Subjects with allergy or hypersensitivity to sulfonamides.

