8.1.4 Expectedness of Adverse Events

An unexpected AE is one for which the nature or severity of the event is not consistent with the applicable study drug information (i.e., the most current version of the IB, the current product labeling for amlodipine tablets, and the current product labeling for celecoxib capsules) or listed in this protocol.

This study will enroll older subjects with existing hypertension. To that end, PTAEs and TEAEs can be expected due to the subjects' age and underlying conditions. These include: hypertension, hypertensive crisis, myocardial infarction, congestive heart failure, stroke both hemorrhagic and ischemic, any adult forms of cancer, and gastrointestinal ulcerations with complications including hemorrhage and perforation.

By definition, PTAEs initiate prior to administration of the first dose of study drugs, and thus a comparison against study drug specific risk information is inappropriate for determining expectedness of PTAEs. Thus, only AEs that can be expected due to subject age and underlying conditions are relevant for the expectedness determination for PTAEs.

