16. HOW SUPPLIED/STORAGE AND HANDLING

17. PATIENT COUNSELING INFORMATION

* Sections or subsections omitted from the full prescribing information are not listed.

FULL PRESCRIBING INFORMATION

WARNING: RISK OF SERIOUS CARDIOVASCULAR AND GASTROINTESTINAL EVENTS

Cardiovascular Thrombotic Events

- Nonsteroidal anti-inflammatory drugs (NSAIDs) cause an increased risk of serious cardiovascular thrombotic events, including myocardial infarction, and stroke, which can be fatal. This risk may occur early in the treatment and may increase with duration of use. [see *Warnings and Precautions (5.1)*]
- CELEBREX is contraindicated in the setting of coronary artery bypass graft (CABG) surgery. [see *Contraindications (4) and Warnings and Precautions (5.1)*]

Gastrointestinal Bleeding, Ulceration, and Perforation

- NSAIDs cause an increased risk of serious gastrointestinal (GI) adverse events including bleeding, ulceration, and perforation of the stomach or intestines, which can be fatal. These events can occur at any time during use and without warning symptoms. Elderly patients and patients with a prior history of peptic ulcer disease and/or GI bleeding are at greater risk for serious (GI) events. [see *Warnings and Precautions (5.2)*]

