2.7 Special Populations

Hepatic Impairment

In patients with moderate hepatic impairment (Child-Pugh Class B), reduce the dose by 50%. The use of CELEBREX in patients with severe hepatic impairment is not recommended [see *Warnings and Precautions (5.5)*, *Use in Specific Populations (8.6)* and *Clinical Pharmacology (12.3)*].

Poor Metabolizers of CYP2C9 Substrates

In adult patients who are known or suspected to be poor CYP2C9 metabolizers based on genotype or previous history/experience with other CYP2C9 substrates (such as warfarin, phenytoin), initiate treatment with half of the lowest recommended dose.

In patients with JRA who are known or suspected to be poor CYP2C9 metabolizers, consider using alternative treatments. [see *Use in Specific Populations* (8.8), and *Clinical Pharmacology* (12.5)].

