5.2 Gastrointestinal Bleeding, Ulceration, and Perforation

NSAIDs, including celecoxib cause serious gastrointestinal (GI) adverse events including inflammation, bleeding, ulceration, and perforation of the esophagus, stomach, small intestine, or large intestine, which can be fatal. These serious adverse events can occur at any time, with or without warning symptoms, in patients treated with CELEBREX. Only one in five patients who develop a serious upper GI adverse event on NSAID therapy is symptomatic. Upper GI ulcers, gross bleeding, or perforation caused by NSAIDs occurred in approximately 1% of patients treated for 3-6 months, and in about 2%-4% of patients treated for one year. However, even short-term NSAID therapy is not without risk.

Risk Factors for GI Bleeding, Ulceration, and Perforation

Patients with a prior history of peptic ulcer disease and/or GI bleeding who used NSAIDs had a greater than 10-fold increased risk for developing a GI bleed compared to patients without these risk factors. Other factors that increase the risk of GI bleeding in patients treated with NSAIDs include longer duration of NSAID therapy; concomitant use of oral corticosteroids, aspirin, anticoagulants; or selective serotonin reuptake inhibitors (SSRIs); smoking; use of alcohol; older age; and poor general health status. Most postmarketing reports of fatal GI events occurred in elderly or debilitated patients. Additionally, patients with advanced liver disease and/or coagulopathy are at increased risk for GI bleeding.

Complicated and symptomatic ulcer rates were 0.78% at nine months for all patients in the CLASS trial, and 2.19% for the subgroup on low-dose ASA. Patients 65 years of age and older had an incidence of 1.40% at nine months, 3.06% when also taking ASA [see *Clinical Studies* (14.6)].

Strategies to Minimize the GI Risks in NSAID-treated patients:

- Use the lowest effective dosage for the shortest possible duration.
- Avoid administration of more than one NSAID at a time.
- Avoid use in patients at higher risk unless benefits are expected to outweigh the increased risk of bleeding. For such patients, as well as those with active GI bleeding, consider alternate therapies other than NSAIDs.
- Remain alert for signs and symptoms of GI ulceration and bleeding during NSAID therapy.
- If a serious GI adverse event is suspected, promptly initiate evaluation and treatment, and discontinue CELEBREX until a serious GI adverse event is ruled out.

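### Exclusion 10 names active peptic ulcer and past GI bleeding but leaves a past non-bleeding ulcer to investigator judgement, although the appended celecoxib label warns of both histories together

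*Protocol*

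**What the plan says.** Exclusion 10 has the same wording in the protocol synopsis and in Section 4.2: "Active peptic ulceration or history of gastrointestinal bleeding". Ulcer is covered only while active. Bleeding is covered at any time in the past.

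Three other criteria could keep out a subject with a healed, non-bleeding ulcer, and none of them mentions ulcer history. Inclusion 5 requires the investigator to judge the subject healthy apart from hypertension, with medical history as one basis. Exclusion 3 is fragile health, which is not defined. Exclusion 4 covers clinically significant screening findings that the investigator considers a safety risk.

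Entry is based on treated hypertension (inclusion 2). No criterion asks for osteoarthritis or any other celecoxib indication, and exclusion 26 removes anyone currently taking an NSAID.

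The boxed warning of the celecoxib label in Appendix G states: "Elderly patients and patients with a prior history of peptic ulcer disease and/or GI bleeding are at greater risk for serious (GI) events". Label Section 5.2 uses the same pairing when it describes risk ("Patients with a prior history of peptic ulcer disease and/or GI bleeding who used NSAIDs") and gives this advice: "Avoid use in patients at higher risk unless benefits are expected to outweigh the increased risk of bleeding". It also says: "However, even short-term NSAID therapy is not without risk".

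**The concern.** The label treats prior ulcer disease and prior GI bleeding as one risk group. Exclusion 10 takes up the bleeding half as a firm rule and leaves the ulcer half to judgement, and the protocol gives no reason for the split.

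The label's advice turns on whether benefit outweighs bleeding risk. A trial subject may happen to have osteoarthritis, but nobody is enrolled for it and current NSAID users are excluded, so there is little benefit to set against the risk. Under the text as written, a subject with a past ulcer whom one investigator considers healthy can be randomized to celecoxib, while another site might turn the same person away.

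What is at stake is the safety of a few subjects. No endpoint, estimate or test is involved.

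**Working it through.** **Comparing the criteria with the label**

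| History | Label (Appendix G) | Protocol |
|---|---|---|
| Past GI bleeding | Boxed warning and 5.2; avoid unless benefit outweighs risk | Named, exclusion 10 |
| Past peptic ulcer, no bleeding | Same warning, same advice | Not named |
| Recent MI | 5.1; avoid unless benefit outweighs risk | Any history of MI named, exclusion 11 |
| Severe heart failure | 5.5; avoid unless benefit outweighs risk | Any history of congestive heart failure named, exclusion 11 |

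None of these four is in the label's contraindication list (Section 4). For the other three the protocol has a named exclusion at least as wide as the label's advice. Past non-bleeding ulcer is the exception.

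**Size of the risk**

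The plan gives no figure for this, so there is none to reproduce. The nearest rate is in label Section 14.6. Among patients with a history of ulcer disease taking celecoxib alone (n=243), the rate of complicated and symptomatic ulcers was 2.56% at 48 weeks, on 400 mg twice daily.

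- Dose ratio: 800 mg/day ÷ 200 mg/day = 4.
- Time scaling, assuming a constant hazard: 48 weeks = 336 days, and 2.56% × 14/336 = 0.107%, about 0.11% per such subject over 14 days.
- Planned celecoxib subjects under 3:3:1: 105 × 3/7 = 45.
- Expected events in the trial = 45 × prevalence × 0.00107. The documents do not give the prevalence of past non-bleeding ulcer, so a range is assumed.

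| Assumed prevalence | Subjects on celecoxib with this history | Expected events |
|---|---|---|
| 2% | 0.9 | 0.001 |
| 5% | 2.25 | 0.002 |
| 10% | 4.5 | 0.005 |

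If the early hazard were five times the average, the 10% row would become 5 × 0.0048 = 0.024. These are total events, not excess over no celecoxib, and they come from four times the trial's daily dose. The label subgroup may also include people who had bled.

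**Recruitment cost of a fixed exclusion**

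Extra otherwise eligible subjects needed to reach 105 randomized = 105/(1 − prevalence) − 105, rounded up.

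- 2%: 105/0.98 − 105 = 2.1, so 3.
- 5%: 105/0.95 − 105 = 5.5, so 6.
- 10%: 105/0.90 − 105 = 11.7, so 12.

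**The case against.** The best defence is that the protocol handles a past ulcer much as the label does. The label asks for case-by-case weighing. The protocol requires a complete medical history (Section 6.1.1), asks the investigator to judge health from it, and appends the full label. No document requires a fixed exclusion. This stands in part: the safeguard exists and will stop some of these subjects. It is weaker here than in practice because there is little benefit to weigh, and the same defence would apply to past bleeding, which the protocol chose to name.

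A second objection is selectivity. Label Section 5.2 also lists corticosteroids, anticoagulants, SSRIs, smoking, alcohol and older age, and the point does not ask for exclusions on those. That is fair as far as it goes. The case here is narrower: exclusion 10 already adopts one half of a pair that the label states together. Older age should be left alone, because Section 1 of the protocol describes the intended patients as older than average.

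Four stronger readings are tempting, and the documents do not support them.

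- *A contraindication is breached.* It is not. Past ulcer is absent from label Section 4.
- *Exclusion 29 shows a general policy of excluding on label warnings.* That criterion reads "Known cytochrome P450 2C9 (CYP2C9) poor metabolizer", and for these patients the label says "initiate treatment with half of the lowest recommended dose". The trial uses a fixed 200 mg over-encapsulated dose, so the half-dose advice cannot be followed. That explains the exclusion without any such policy.
- *The protocol itself foresees this harm.* Section 8.1.4 does list "gastrointestinal ulcerations with complications including hemorrhage and perforation", but as part of an expectedness list for adverse event reporting, alongside stroke and cancer. It says nothing about whether exclusion 10 is adequate.
- *The label's greater than 10-fold bleeding risk applies to these subjects.* That figure is for ulcer disease and/or bleeding combined and is not specific to a non-bleeding ulcer.

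**Conclusion.** The gap in the text is real, and no other criterion closes it: a past non-bleeding ulcer depends on discretion, while its counterpart in the label's warning is a named exclusion. The consequence is very small, with an expected count well below one event even under the pessimistic early-hazard assumption. Exposure is 14 doses at the labelled once-daily osteoarthritis dose, and other NSAIDs are barred through Day 28 (Section 5.6). The estimate rests on a constant hazard, a rate taken from a higher dose and a different population, and assumed prevalences, so it shows an order of magnitude only. The point is minor: an inexpensive improvement in subject protection with no bearing on the trial's conclusions.

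**What to change.** In the synopsis and in Section 4.2, change exclusion 10 to: *Active or history of peptic ulceration, or history of gastrointestinal bleeding.*

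No new procedure is needed, because the complete medical history is already taken at the initial screening visit. The only cost is recruitment: at most about 3, 6 or 12 additional otherwise eligible subjects at an assumed prevalence of 2%, 5% or 10%. This is an upper bound, since investigators would already turn away some of these people. The SAP does not need to change.

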1. BACKGROUND

KIT-302 is an oral fixed combination drug product (FCDP) consisting of the calcium (Ca) channel blocker antihypertensive drug amlodipine besylate and the non-steroidal anti-inflammatory drug (NSAID) celecoxib. Amlodipine besylate and celecoxib are marketed in the United States (US) and worldwide as individual branded and generic prescription drug products, and as combination drug products with other prescription drugs, in the case of amlodipine. Kitov Pharmaceuticals, Ltd. (Kitov) is developing KIT-302 as a “convenience reformulation” FCDP intended to facilitate and improve patient compliance with the once a day (qd) administration of its individual components, amlodipine besylate and celecoxib, when used together for the intended patient population.

Long-term treatment with celecoxib is most commonly used in treating patients with osteoarthritis. This population is generally more aged than an average cross-section of people. It is therefore to be expected that a significant percentage of these patients will also have hypertension. Thus, it can be anticipated that a significant number of patients requiring chronic celecoxib therapy will also require chronic antihypertensive therapy. KIT-302 is intended to treat these patients.

The proposed indications for KIT-302 are a subset of those for the combined labeling of the individual marketed prescription drug products (i.e., amlodipine besylate tablets and celecoxib capsules), and in particular, a subset of those for which qd administration is an option. Thus, the proposed indications in the usage section of the KIT-302 product labeling are anticipated to read as follows: “KIT-302 is indicated for the treatment of hypertension, to lower blood pressure, in patients who also require the use of a NSAID for relief of the signs and symptoms of osteoarthritis. Lowering blood pressure reduces the risk of fatal and nonfatal cardiovascular events, primarily strokes and myocardial infarctions.”

The formulation of KIT-302 consists of amlodipine besylate and celecoxib co-formulated in a single immediate release tablet. The dosage form was developed so that it will show bioequivalence (BE) to the individually marketed prescription amlodipine besylate tablets and celecoxib capsules given together. The strengths of the KIT-302 tablets reflect the three different possible combinations of the strengths of individual marketed prescription drug products for the proposed indications.

The previous human experience with the KIT-302 formulation (i.e., the FCDP) is limited to bioavailability studies in healthy volunteers under fasted (Study No. DXE-P6-039) and fed states (Study No. DXE-P6-127 and Study No. TRC 009/10219). However, an efficacy study (Study No. KIT-302-03-01) was conducted using the individual components, amlodipine besylate and celecoxib, and the latter have been approved and marketed in the US and worldwide for many years (amlodipine besylate tablets were first approved in 1992 and celecoxib capsules were first approved in 1998), and have well-established clinical safety profiles.

Amlodipine besylate tablets are recognized as being generally safe for patients. Post-marketing surveillance has confirmed the safety of amlodipine besylate tablets. While generally regarded as safe, celecoxib and other NSAIDs can cause gastrointestinal ulcerations and cardiovascular problems. Copies of the prescribing information for prescription amlodipine besylate [Norvasc[®] (amlodipine besylate) tablets] and prescription celecoxib [Celebrex[®] (celecoxib) capsules] are

included in Appendices F and G, respectively. These product labelings list the adverse events (AEs) that can be expected from the drug substances.

The concomitant oral administration of labeled doses of amlodipine besylate and celecoxib does not appear to present any new safety issues in terms of potential additive or synergistic pharmacodynamic, pharmacokinetic (PK), or toxicological interactions. The FCDP is not anticipated to produce systemic exposures to either drug greater than those associated with current clinical use of either drug administered alone or in combination.

Study No. DXE-P6-039 and Study No. DXE-P6-127 demonstrated that a single oral dose of the highest strength KIT-302 dosage form (10 mg amlodipine besylate/200 mg celecoxib) is BE to the individual commercially available products given together (10 mg amlodipine besylate tablet + 200 mg celecoxib capsule) in healthy volunteers under fasted and fed conditions, respectively. The combination was well tolerated, and no new AE findings occurred relative to the individual prescribing information for amlodipine besylate tablets and celecoxib capsules.

The findings of Study No. DXE-P6-127 were consistent with the earlier pilot BE study in healthy males under fed conditions (Study No. TRC 009/10219). In the latter study, two prototype formulations of KIT-302 were evaluated, and prototype formulation 1 was shown to be BE to the individual commercial drugs given together. Prototype formulation 1 was pursued for the manufacture of registration stability lots of KIT-302 FCDP and one of the resulting lots was used for the full BE studies (Study Nos. DXE-P6-039 and DXE-P6-127). As with the full BE studies, the pilot BE study showed the formulation to be well tolerated, with no new AE findings.

In November 2015, Kitov completed a phase 3 pivotal study (KIT-302-03-01) comparing amlodipine monotherapy at a dose of 10 mg/day, with the combination of the components of KIT-302 at a dose of 10 mg amlodipine plus 200 mg celecoxib/day. The study also included a double placebo arm and a celecoxib monotherapy arm (200 mg/day). For the combination arm, two separate capsules were used, one containing the commercial amlodipine tablet and one containing the commercial celecoxib capsule. Each of the commercial formulations were individually OE, as were the matched placebo tablets and capsules to allow for blinding.

One hundred fifty-two (152) adult subjects with newly diagnosed hypertension who required pharmacological therapy to control their hypertension were randomized 1.5:1.5:1:1 to one of the four treatment arms (amlodipine/celecoxib: 10/200 mg, 10/0 mg, 0/200 mg, and 0/0 mg) and were administered study drug once a day for 14 days. Subjects underwent 24-hour ambulatory blood pressure monitoring at baseline, during the initial 24 hours of therapy, after one week of therapy, and after two weeks of therapy.

The mean changes in average daytime (9:00 to 21:00) ambulatory systolic blood pressure (SBP_{day}), average daytime (9:00 to 21:00) diastolic blood pressure (DBP_{day}), average night-time (01:00 to 06:00) ambulatory systolic blood pressure (SBP_{night}), and average night-time (01:00 to 06:00) diastolic blood pressure (DBP_{night}) from baseline to end of therapy are listed below. Subjects in the amlodipine monotherapy arm had a mean reduction in SBP_{day} of 8.8 ± 8.1 mm Hg after 14 days of treatment, whereas subjects in the amlodipine + celecoxib arm had a mean reduction of 10.6 ± 9.2 mm Hg. The combination was shown to be statistically non-inferior to amlodipine alone ($p < 0.001$), and the primary efficacy endpoint of the study was successfully achieved. Further, the

change in SBP_{day} showed a synergistic effect with the combination over amlodipine monotherapy. The change in DBP_{day} showed a similar synergistic effect with the combination over amlodipine monotherapy and this synergy was even greater with respect to the SBP_{night} and DBP_{night} changes. Celecoxib monotherapy did tend to raise blood pressure (BP), not lower it, as expected, although statistical significance was not achieved.

**Changes in Blood Pressure from Baseline to End of Therapy
(Mean ± Standard Deviation mm Hg)**

	SBP_{day}	DBP_{day}	SBP_{night}	DBP_{night}
Placebo	-2.1 ± 8.2	-0.3 ± 5.4	-1.4 ± 9.2	0.0 ± 6.2
Celecoxib	-0.5 ± 8.8	-1.5 ± 5.1	-1.7 ± 12.3	0.3 ± 7.1
Amlodipine	-8.8 ± 8.1	-5.5 ± 5.1	-6.4 ± 11.4	-3.2 ± 7.8
Amlodipine + Celecoxib	-10.6 ± 9.2	-7.5 ± 6.4	-10.5 ± 10.6	-7.0 ± 8.6

Consistent with the known potential of celecoxib to alter renal physiology, the celecoxib monotherapy arm showed a trend towards worsened function as measured by the change in serum creatinine from baseline to end of therapy relative to the placebo arm. In contrast, the amlodipine monotherapy showed a trend towards improved renal function compared to placebo. Further, the combination of the two (amlodipine + celecoxib) showed a trend towards improved renal function that was greater than that noted for amlodipine alone.

The oral administration of 10 mg amlodipine besylate and 200 mg celecoxib, either individually (i.e., with a matched placebo) or in combination once daily for 14 days in adult subjects with newly diagnosed hypertension who required pharmacological therapy was well tolerated. No deaths or serious adverse events (SAEs) were reported in Study No. KIT-302-03-01. Of the AEs that were considered to be related to the study drugs (i.e., assigned as either a suspected adverse reaction or adverse reaction by the Investigator), all were mild in severity, except for a single incidence of headache that was moderate in severity. Further, all of these AEs fully resolved.

Study No. KIT-302-03-01 also included the collection of PK blood samples at the end of the study (i.e., steady state; Day 14) in a subset of the trial population to evaluate for drug-drug interactions. The analyses showed that amlodipine had no statistically significant effect on the plasma levels of celecoxib. However, celecoxib reduced the plasma levels of amlodipine by approximately a third ($p < 0.001$). The mechanism for the enhancement in efficacy (lowering of BP) and trend towards improved renal function despite the reduction in the plasma concentration of amlodipine is currently unknown. Kitov hypothesizes that celecoxib prevents the fluid retention amlodipine causes (it acts in a manner similar to a diuretic) as evidenced by the reduced rate of oedema reported in patients receiving the combination therapy in the trial (8.2%) as opposed to those receiving amlodipine monotherapy (15.6%). Such a diuretic type effect would be expected to lower BP.

For further details regarding Study No. KIT-302-03-01 and the bioavailability studies, please refer to the most current version of the Investigator's Brochure (IB) for KIT-302.

This study will be performed in compliance with the current ICH guidelines for GCP and all applicable regulatory requirements.

